Study Protocol

ENLIGHTEN: Assessment of quality improvement in the International Severe Asthma Registry

Date:
10 Feb 2025

International Severe Asthma Registry (ISAR)
Study Protocol: ENLIGHTEN: v3.0, 5 Feb 2025

Chief Investigator:

[name], Professor of Primary Care Respiratory Medicine and OPRI Director
[contact]
Office number: [name]
Skype ID: [name]
Email: [contact]

Project Coordinator:

[name], Research & Operations Director
Observational & Pragmatic Research Institute
Office address: [name]
Direct number: [contact]
Email: [contact]

Study Sponsor:

OPRI UK

Primary Contact:

Name: [contact]

TITLE	ENLIGHTEN: Assessment of quality improvement in the International Severe Asthma Registry
Subtitle	
Protocol version number	V3.0
Medicinal product	Not applicable
Product code	Not applicable
Marketing authorisation holder	Not applicable
Marketing authorisation number	Not applicable
Study aims and objectives	
The aim of this study is to evaluate the quality of the International Severe Asthma Register (ISAR) data over time and during quality initiatives by investigating changes in process measures (completeness of key research data) and clinical measures (long-term oral corticosteroid [LTOCS] prescribing and initiation of biologics). Specific objectives are:
 
 1. To investigate the proportion of patients in ISAR with 90% and 100% completeness of key research variables (as voted on in a 2023/24 Delphi exercise) from 1 May 2017 to the latest date available. 2. To investigate completeness of recording of all core variables in ISAR (as voted during the 2024 Delphi exercise). 3. To investigate how: 
 a. the proportion of patients in ISAR who are prescribed LTOCS vary over time b. the proportion of patients on LTOCS that are stopped/reduced vary over time. 4. To investigate initiation to biologic treatments by severity of asthma indicators over time.
Countries of study	All countries/sites contributing to the ISAR initiative who have consented for their data to be used in research
Author(s)	[name], [name], [name], [name], [name], [name], [name]

Table of Contents

List Of Abbreviations	5	Deleted: 4
1. Background	6	Deleted: 5
2. Study Aims and Objectives	7	Deleted: 7
2.1. Study Aims	7	Deleted: 7

Healthcare registry data require robust quality improvement initiatives as they have the potential to provide a rich source of surveillance data on healthcare patterns, clinical decision making and delivery of interventions that can, ultimately, improve patient outcomes (3). However, registry data also rely heavily on understanding how the data were derived and why they were recorded so that its users can interpret the results meaningfully. For example, when using registry data that combine information on patients from different sites and countries, consideration needs to be made of relevant healthcare systems and specific national policy initiatives.

This study investigates the quality of the International Severe Asthma Register (ISAR) data over time and during key policy and quality improvement initiatives of a longitudinal, real-life data registry for patients with severe asthma (4). The ISAR provides a useful framework through which other quality improvement initiatives can be developed as it is underpinned by data quality goals that align with stakeholder needs and the needs of patients with severe asthma. Such goals include high level of completeness in the collection of core variables and key research variables, which help to inform both day-to-day clinical decision-making (e.g. by identifying patients, who may benefit from further monitoring or treatment), and promote severe asthma research (e.g. treatment efficacy/effectiveness). At the forefront of the ISAR initiative's original (and continuing) mission was to reduce long-term oral corticosteroid (LTOCS) exposure (5) and facilitate the provision of an international consortium for research collaboration in respiratory medicine and patient care (6). A minimum core set of variables for the ISAR was developed in 2017 as part of a modified Delphi process consisting of 3 iterative rounds and two face-to-face meetings with a panel of 27 international experts in the field of severe asthma research (7). A follow-on Delphi exercise was conducted in 2023 to identify key variables for use in research, which was further refined in 2024. Additional quality improvement plans for the ISAR were introduced from 2023. These included the introduction of a data quality report, a country-specific data quality dashboard, face-to-face meetings on

data quality issues, and (optional for some countries) an optimised electronic case report form (eCRF).

2. Study Aims and Objectives

2.1. Study Aims

ENLIGHTEN aims to explore the quality of ISAR data over time and during key policy and improvement change initiatives by investigating changes in process measures (completeness of key research data) and clinical practice (severity indicators of biologic initiation) and outcomes (long-term oral corticosteroid [LTOCS] prescribing). Although based on ISAR's quality improvement implementation plan and target goals for each country, it forms a distinct research exercise to look more broadly at the impact of the ISAR collaboration on data quality and patient care. The findings will be presented in aggregated form, stratified by country, where appropriate.

The aim of the ENLIGHTEN project is to investigate the quality of the International Severe Asthma Register (ISAR) data over time and during key practice change initiatives in relation to completeness of key research data and patient outcomes. As well as data quality, we also aim to investigate how data has changed on ISAR in terms of changes in clinical practice.

4.1. Data Sources

This study uses data on eligible patients contributing to the ISAR programme from those countries that have consented for their data to be used for research.

4.2. Inclusion and Exclusion Criteria

Inclusion Criteria

- Patient meets criteria for severe asthma:
 - On Global Initiative for Asthma (GINA 2021) Step 5 (8)
 - Uncontrolled on GINA Step 4, at least one of the following:

- poor symptom control: asthma control questionnaire ACQ>1.5, ACT<20 or "not well controlled" by National Education and Prevention Program [NAEPP]/GINA guidelines (8,9)
- airflow limitation: after appropriate bronchodilator withhold Forced expiratory volume in one second (FEV1) <80% predicted (in the face of reduced FEV1/forced vital capacity [FVC] defined as less than the lower limit of normal)
- serious exacerbations: at least one hospitalisation, intensive care unit (ICU) stay or mechanical ventilation in the previous year
- frequent exacerbations: two or more bursts of systemic corticosteroids (>3 days each) in the previous year

Exclusion Criteria

- For Objective (3), patients will be excluded if they have an unknown LTOCS status (objective 3 – although we will look at 'unknown' LTOCS that has been completed retrospectively to assess any potential for bias), if they have information on only 1 visit, and/or they are not taking LTOCS at their baseline visit (defined by first visit with LTOCS=yes). For Objective (4), patients will be excluded if they have unknown biologic status and/or none of the asthma severity indicators at baseline (defined by first visit with asthma severity indicator=yes)
- Patients (from some countries/regions) who have not consented for their data to be used for research purposes and/or data that have been approved for specific studies only.

5. Study Variables and Study Outcome Definitions

Objective 1: Proportion of patients on the ISAR with 100% completeness of key research variables from 2017 to latest date available

Outcome: Proportion of patients meeting 100% completeness of key research variables by patient status (i.e. new patients and follow-up visits)

Exposure: Time (calendar year and pre-specified periods of change)

Covariates: Country (numbers allowing), Country-specific factors (method of data provision, healthcare setting, date of participating in ISAR), visit-specific factors

We will focus on key research variables, as voted for in the 2023/24 Delphi exercise. For first visits or where patient starts or switches a biologic (**KPR visits**), 16 variables will be investigated (see **Table 1**). For **re-review (RR)** visits, 11 variables will be investigated.

We will divide the visit dates into calendar years and assess the proportion of all individuals meeting the criteria for 90% and 100% key research variables to assess whether there are any changes/trends over time. We will also investigate before and after completeness over key periods (e.g. introduction of quality improvement initiatives [period from introduction of data quality [DQ] dashboards, reports and face-to-face meetings], changes in data capture systems) where we might expect completeness to change. As well as looking at changes by calendar year for the most recent complete data set, we will use snapshot data to assess completeness and accuracy of data in different snapshot periods. This process will allow for the evaluation of backdated quality improvements in the data. For example, 2021 data from 2024 will be compared with 2021 data captured in 2021, 2022 and 2023 (and different quarters within this period where we might expect to see changes).

Table 1. Key research variables as voted for in Delphi by key prior review (KPR) and re-review (RR) visits

KEY	KPR & RR	KPR ONLY	RR ONLY
-----	----------	----------	---------

Category	Variable Field Name	Key prior review	Re-review
DOV	Date of visit		
AGE, GENDER, HEIGHT & WEIGHT	Date of Birth		
	Gender		
	Weight		
	Height		
SMOKING STATUS	What is the current smoking status of the patient?		
ASTHMA ONSET	At what age did the patient's asthma symptoms begin? Whole years or months if < 1 year		
EXACERBATION	Number of exacerbations requiring rescue (systemic/oral) steroids in the past 12 months?		
HOSPITAL ADMISSION	Total number of hospital admissions for asthma in the past 12 months?		
CHRONIC RHINOSINUSITIS	Indication of: Chronic Rhinosinusitis		

NASAL POLYPS	Indication of: Nasal Polyps		
HIGHEST BLOOD EOSINOPHIL COUNT	What is the Highest Blood Eosinophil Count (within the past year)? Also built from blood eosinophil records if missing		
IGE COUNT	What is the IgE Count (latest)		
POST-BD-FEV1 or ON TREATMENT FEV1	Post-bronchodilator FEV1		
ASTHMA CONTROL	Asthma (symptom) Control		
LTOCS AND DAILY DOSE	Is the patient prescribed Maintenance Oral Steroids?		
	Daily dose of Maintenance Oral Steroids		
PRESCRIPTION ICS+LABA/ICS/LABA/LAMA/THEO/LTRA	Is the patient on a prescription for ICS+LABA combination therapy?		
	Is the patient on a prescription for ICS (only)?		
	Is the patient on a prescription for LABA (only)?		
	Is the patient on a prescription for LAMA?		
	Is the patient on a prescription for Theophyllines?		
	Is the patient on a prescription for Leukotrine Receptor Antagonist (LTRA)?		
	Is the patient on a prescription for Macrolide Antibiotic Treatment?		
BIOLOGIC	Prescription for Anti-Interleukin 4 (Anti-IL4) Treatment?		
	Prescription for Anti-Interleukin 5 (Anti-IL5) Treatment?		
	Prescription for Anti-IgE Treatment?		
	Prescription for Anti-TSLP Treatment?		
BIOLOGIC START DATE	Start Date of Anti-Interleukin 4 (Anti-IL4) Treatment?		
	Start Date of Anti-Interleukin 5 (Anti-IL5) Treatment?		
	Start Date of Anti-IgE Treatment?		
	Start Date of Anti-TSLP Treatment?		
REASON FOR SWITCH	Reason for biologic switch		

Objective 2: Completeness of recording of core variables in ISAR over time

Outcome: Proportion of core variables that are complete for each patient

Exposure: Time (calendar year and pre-specified periods of change)

Covariates: Age, gender, country, country-specific factors, visit-specific factors

We will investigate the percentage of patients with 90% complete core variables in ISAR over time. The completeness of individual core variables will also be investigated, as well as

the proportion of individuals that meet criteria for $\geq 90\%$ completeness of core variables. There are 38 core variables in the ISAR, as voted for in the Delphi 2017 exercise. These are shown in **Appendix 1** (Section 13.1) along with some more information about the ISAR schedules. We will also investigate patient characteristics associated with completeness of data for targeted strategies.

Objective 3: Differential characteristics and proportion of patients on LTOCS in the ISAR registry over time

Outcome: Proportion of patients on LTOCS (at visit)

Exposure: Time (calendar year and pre-specified periods of change)

Covariates: Age, gender, country, country-specific factors

The characteristics of patients in the ISAR registry who are prescribed LTOCS are likely to change with policy initiatives, awareness of serious adverse events, increased knowledge about asthma among participating sites, and biologic availability. ISAR may also have prompted behaviour change among clinicians who treat patients with severe asthma thereby affecting their treatments and/or outcomes. We will assess trends in LTOCS use over time, adjusting for age and gender, and stratifying by country and country-specific factors (e.g. participation in ISAR consortium, data capture system). We will also evaluate proportion and time to stopping/reducing the dose ($\leq 5\text{mg}$) of LTOCS to assess differences in clinical practice over calendar time.

Objective 4: Severity of asthma in those initiating biologic treatment over time

Outcome: Initiation of biologic treatment by asthma severity indicator

Exposure: Time (calendar year and pre-specified periods of change)

Covariates: Age, gender, country-specific factors

We will investigate and describe initiation of first biologic treatment by asthma severity indicator over calendar time, also adjusted for age and gender. We will further explore whether this changes as quality of data improves and/or in response to key practice change initiatives (quality improvement, seminal papers). Asthma severity indicators will be defined using each of the following criteria: LTOCS use; pre-visit exacerbation(s); asthma control status; and lung function [FEV₁% predicted] (12).

6. Statistical Analysis

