Objective 2: Completeness of recording of all core variables in ISAR

Annual trends and changes in the proportion of core variables will be investigated in ISAR, also stratifying by country and provision of data method. The completeness of individual core variables will also be investigated to assess the variables that are least likely to be complete.

We will use a combination of joinpoint regression (to investigate trends) and ITSA (to investigate pre-specified inflection time points) with variation in country modelled as a random effect for this component of the analysis, also stratifying by data capture method. **Appendix 1** (Section 13.1) shows the complete list of core variables in ISAR.

Objective 3: Differences in the proportion of patients in ISAR who are prescribed LTOCS varies over time, and the characteristics of these patients

Trends in the proportion of patients with a LTOCS prescription in a given year (i.e. yes/no) and average dose of LTOCS will be described and plotted by calendar year using a combination of joinpoint regression and ITSA to analyse significant changes in trends, also stratifying by country-specific data capture method. For those on LTOCS, we will also investigate the probability of stopping/reducing LTOCS dose (<5mg) using time-to-event analysis (non-parametric [Kaplan-Meier] and flexible parametric methods). Patient characteristics for people with and without missing/incomplete data on LTOCS will also be compared.

Objective 4: Trends in the severity of asthma indicators in those initiating biologic treatment over time

The probability of initiating biologic treatments by asthma severity indicator and calendar year will be investigated using time-to-event analyses (non-parametric and flexible parametric models).

7. Regulatory and Ethical Compliance

This study was designed and shall be implemented and reported in accordance with the criteria of the “European Network Centres for Pharmacoepidemiology and Pharmacovigilance (ENCePP)” and follows the ENCePP Code of Conduct (EMA 2014). Once a final version of the protocol has been agreed and reviewed by the advisory group, this study will be registered with ENCePP (www.encepp.eu).

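### Objective 3(ii) merges stopping with a dose-based reduction, but entry is screened on LTOCS status and not on dose, so the stop/reduce trend can reflect dose recording as well as practice

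*Protocol*

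**What the plan says.** Section 4.2 of the protocol sets entry to Objective 3. On missing data it says: "For Objective (3), patients will be excluded if they have an unknown LTOCS status". The other exclusions apply to patients "if they have information on only 1 visit, and/or they are not taking LTOCS at their baseline visit (defined by first visit with LTOCS=yes". None of these refers to dose.

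The outcome does use dose. Section 5, Objective 3, says "We will also evaluate proportion and time to stopping/reducing the dose", with the threshold written as at most 5 mg, in order to assess differences in practice over calendar time. Section 6.3, Objective 3, says "we will also investigate the probability of stopping/reducing LTOCS dose (<5mg) using time-to-event analysis", which is a strict inequality.

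Table 1 in Section 5 groups two fields under one LTOCS item: whether maintenance oral steroids are prescribed, and "Daily dose of Maintenance Oral Steroids". The item counts as a key research variable at both visit types.

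The exposure for Objective 3 is calendar year and pre-specified periods of change. Under Objective 1, Section 5 describes the periods of quality initiatives and data-capture changes as ones "where we might expect completeness to change".

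Two checks on missing LTOCS data are planned. Section 4.2 adds "although we will look at 'unknown' LTOCS that has been completed retrospectively to assess any potential for bias", and Section 6.3 adds "Patient characteristics for people with and without missing/incomplete data on LTOCS will also be compared".

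**The concern.** A patient with LTOCS recorded as yes and a blank dose meets the entry rule. From then on, a stop can be seen from the status field alone, but a reduction short of stopping cannot be seen until a dose is entered. The entry rule screens one of the two fields that the event needs.

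This matters because time is the exposure. If dose recording improves with the 2023 quality programme, ascertainment of the reduction component changes over the same period in which the analysis looks for a change in practice. A shift in the combined rate could then be read as more steroid-sparing care when part of it is fuller data entry. In a study whose subject is data completeness, this threat bears directly on the clinical conclusion.

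**Working it through.** The protocol gives no dose completeness, stop rate or reduction rate, so there is no figure of its own to reproduce. All inputs below are assumptions, and true practice is held constant throughout.

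**1. Does the direction depend on how a blank dose is handled?** Let s be the true proportion stopping, m the true proportion reducing without stopping, and q the probability that dose is recorded when LTOCS is yes.

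- Rule A, blank dose counts as no event: s + m·q.
- Rule B, follow-up visits with LTOCS yes and blank dose are dropped while stops stay evaluable: (s + m·q) / (s + (1 − s)·q).
- Rule C, patients without dose are left out regardless of outcome: s + m.

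With s = 0.15 and m = 0.15 (true rate 30%), and q rising from 0.60 to 0.90:

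- A: 0.15 + 0.15 × 0.60 = 24.0%, rising to 0.15 + 0.15 × 0.90 = 28.5%.
- B: 0.24 / (0.15 + 0.85 × 0.60) = 36.4%, falling to 0.285 / (0.15 + 0.85 × 0.90) = 31.1%.
- C: 30.0% at both.

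Other values of s and m, same change in q:

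| s, m | Rule A | Rule B |
|---|---|---|
| 0.20, 0.10 | 26.0% to 29.0% | 38.2% to 31.5% |
| 0.10, 0.25 | 25.0% to 32.5% | 39.1% to 35.7% |
| 0.15, 0.30 | 33.0% to 42.0% | 50.0% to 45.9% |

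Rule A gives +3 to +9 points and rule B a fall each time. A shift from 24.0% to 28.5% would reach two-sided 5% significance with probability of about 63% at 1,000 patients per period and 90% at 2,000.

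**2. What if patients with a blank baseline dose and a low later dose are counted as reduced?** Suppose 40% of patients are already at or below the threshold at baseline, that they leave the cohort if that dose is recorded, and that they stay if it is blank. With s = m = 0.15 the observed rate is 32.8% at q = 0.60, 33.7% at 0.70, 32.4% at 0.90 and 30.0% at 1.00. It rises and then falls.

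**3. How large is the artefact over follow-up under rule A?** Visits are 6-monthly, with K visits by the time point. Stopping (rate a per year) and reduction (rate b per year) are independent with constant rates, and a reduction is seen at the first visit from its occurrence onward with a recorded dose.

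- Stopping: S = 1 − exp(−0.5·a·K).
- Reduction seen: R = Σ p_k·[1 − (1 − q)^(K − k + 1)], summed over k = 1 to K, with p_k = exp(−0.5·b·(k − 1)) − exp(−0.5·b·k).
- Observed stop/reduce: 1 − (1 − S)(1 − R).

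For a = 0.10, b = 0.20, K = 2: p_1 = 0.0952, p_2 = 0.0861, S = 0.0952.

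- q = 0.5: R = 0.0952 × 0.75 + 0.0861 × 0.5 = 0.1144; observed 1 − 0.9048 × 0.8856 = 19.9%.
- q = 0.9: R = 0.0952 × 0.99 + 0.0861 × 0.9 = 0.1717; observed 1 − 0.9048 × 0.8283 = 25.1%.

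| Rates per year | Time | q = 0.5 | q = 0.9 | Artefact |
|---|---|---|---|---|
| stop 0.10, reduce 0.20 | 12 months | 19.9% | 25.1% | +5.2 points |
| stop 0.10, reduce 0.20 | 36 months | 54.7% | 58.9% | +4.2 points |
| stop 0.20, reduce 0.10 | 12 months | 23.0% | 25.5% | +2.5 points |

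Stopping does not involve q: with a = 0.10 it is 9.5% at 12 months at any level of dose recording.

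**4. Does requiring a recorded baseline dose remove the artefact?** The same model was simulated for reduction alone (stop 0.10, reduce 0.20), with three years of follow-up and censoring at the last visit with a recorded dose. As q goes from 0.5 to 0.9, the Kaplan-Meier estimate moves from about 12% to 17% at 12 months and from about 49% to 45% at 36 months. The artefact remains and changes sign, because blanks delay detection and censoring itself depends on recording.

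**The case against.** The strongest reply is that handling of a blank dose in a time-to-event endpoint normally belongs in the SAP, which is not at hand, so its absence from the protocol is no fault. That stands, and the point does not rest on it. It rests on what the protocol does fix: one combined event, an entry rule that screens on status only, and an exposure along which completeness is expected to change.

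A reader might go further and infer that the stop/reduce rate will rise as recording improves. The documents do not support that. It needs a rule that a blank dose keeps the patient at risk with no event, and no section states one. Other rules give a flat or falling trend. Nor does the text say that a blank baseline followed by a low dose counts as a reduction; the word reducing can be read as requiring an earlier dose.

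The planned checks also deserve credit. Status and dose form one item in Table 1, so the comparison of patients with incomplete LTOCS data can fairly be read to cover a blank dose. Objective 2 looks at completeness of individual core variables, and LTOCS trends are stratified by data-capture method. Historical snapshots are assigned to Objectives 1 and 2 in Section 3, and in Section 6.3 to trends in reporting for all objectives but the fourth. These could reveal changing dose recording, but they are descriptive and change neither the risk set nor the event.

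**Conclusion.** The point holds as a risk of confounding whose direction is not determined. The combined stop/reduce trend can mix recording with practice. An upward artefact is most plausible if a blank dose counts as no event. In that case, with recording rising from 50% to 90%, it is about +2.5 to +5 points at 12 months, depending on whether stopping or reduction is the commoner event, and about +4 points at 36 months for the rates that give +5 at 12 months. These sizes rest on assumed rates, 6-monthly visits and assumed recording levels.

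The problem is confined to the reduction component. Stopping is read from status and is unaffected by dose recording, so Objective 3 as a whole is not undermined. Separately, Sections 5 and 6.3 disagree on whether exactly 5 mg counts as a reduction.

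**What to change.** - In Sections 5 and 6.3, make stopping (LTOCS yes to no, among patients with known status) a separate endpoint, and draw the change-in-practice conclusion from it.
- Report dose reduction as a secondary, descriptive component in patients with a recorded baseline dose, and state that condition in Section 4.2. Show dose completeness by calendar year beside it.
- Say plainly that the baseline-dose condition lessens ambiguity about the starting dose but does not remove the recording artefact. Simply dropping visits with a blank dose is no remedy: it over-represents stops and can reverse the bias, as rule B shows.
- Reconcile the two wordings of the 5 mg threshold in Sections 5 and 6.3.

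The cost is a change of wording, a smaller cohort for reduction, and a weaker conclusion about reduction. No new data collection is needed.

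### Objective 3 excludes patients with unknown LTOCS status while recording is expected to change along the exposure axis, so recording that changes differently for users and non-users can create a false LTOCS trend in either direction

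*Protocol*

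**What the plan says.** Protocol Section 4.2 sets the analysis population for Objective 3: "patients will be excluded if they have an unknown LTOCS status". The same sentence recognises the risk and plans a check, a look at unknown "LTOCS that has been completed retrospectively to assess any potential for bias". Section 6.3, under Objective 3, adds a second: "Patient characteristics for people with and without missing/incomplete data on LTOCS will also be compared".

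Section 5 defines the measure for Objective 3 as "Outcome: Proportion of patients on LTOCS (at visit"), against "Exposure: Time (calendar year and pre-specified periods of change"). Section 6.3 models the odds of LTOCS use before and after intervention periods with a logistic mixed model that has a random intercept for country.

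On recording, Table 1 in Section 5 lists the item "Is the patient prescribed Maintenance Oral Steroids" among the key research variables at both visit types. Section 5, under Objective 1, describes quality initiatives and changes of data-capture system as periods "where we might expect completeness to change". Section 1 dates the initiatives: "Additional quality improvement plans for the ISAR were introduced from 2023".

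**The concern.** Objective 3(i) asks what proportion of registry patients are prescribed LTOCS and how that varies over time. Excluding unknowns answers a narrower question: the proportion among patients whose status was recorded. When recording is stable, the gap between the two is roughly constant and a trend survives. Here the protocol expects completeness of the key variables to move over the same years and around the same initiatives that define the exposure. An initiative could therefore change who enters the denominator, and the result could be read as a change in prescribing.

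A random country intercept does not absorb a change in recording within a country over time, and stratifying by data-capture method does not address a change within a stratum. The bootstrap intervals describe sampling variation, not this bias. Reducing LTOCS exposure is part of the registry's stated mission (Section 1), so a false fall would be easy to accept and a false rise would mislead just as much.

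**Working it through.** **Inputs.** The protocol states no LTOCS prevalence, unknown-status rate, effect size or power for Objective 3, so there is no figure of its own to reproduce. Every rate below is an assumption, chosen to show a range.

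**Formula.** Let p be the true proportion on LTOCS, rY the probability that status is recorded for a user, and rN the same for a non-user.

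- Known-only proportion = p·rY / (p·rY + (1 − p)·rN).
- Known-only odds = [p/(1 − p)] × (rY/rN).
- With p constant, the spurious odds ratio, late versus early, is (rY/rN)late ÷ (rY/rN)early. It does not depend on p.
- Unknown share = p(1 − rY) + (1 − p)(1 − rN).

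**Results with true use constant at 30%.**

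| Scenario (recording in users/non-users, early → late) | Known-only, early → late | Spurious odds ratio | Unknown share, early → late |
|---|---|---|---|
| A: 95%/80% → 95%/90% | 33.7% → 31.1% | 0.89 | 15.5% → 8.5% |
| B: 95%/60% → 95%/90% | 40.4% → 31.1% | 0.67 | 29.5% → 8.5% |
| C: 70%/70% → 95%/95% | 30.0% → 30.0% | 1.00 | 30.0% → 5.0% |
| D: 60%/95% → 95%/98% | 21.3% → 29.4% | 1.53 | 15.5% → 2.9% |

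Scenario B in full: early 0.285/(0.285 + 0.42) = 40.4%; late 0.285/(0.285 + 0.63) = 31.1%. Scenario D in full: early 0.18/(0.18 + 0.665) = 21.3%; late 0.285/(0.285 + 0.686) = 29.4%.

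Scenario B at other prevalences: with p = 20%, 28.4% → 20.9%; with p = 40%, 51.4% → 41.3%.

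**What this shows.** A and B give a false fall of 2.6 and 9.3 points, D gives a false rise of about 8 points, and C gives no bias although the unknown share drops by 25 points. What matters is whether the ratio rY/rN changes over time, not whether recording improves overall.

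**Bounds with unknowns kept in.** Counting all unknowns as no gives p·rY; counting all as yes gives p·rY plus the unknown share.

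- Scenario B: early 28.5% to 58.0%, late 28.5% to 37.0%.
- Scenario D: early 18.0% to 33.5%, late 28.5% to 31.4%.

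In both, the late range lies inside the early one, so the data would not establish the fall or the rise that the known-only figures suggest.

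**Why one bound is not enough.** Suppose true use falls from 30% to 20% while recording among users rises from 60% to 95%. Counting all unknowns as no gives 0.30 × 0.60 = 18%, then 0.20 × 0.95 = 19%. A real fall of 10 points disappears.

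**The case against.** Several counter-arguments have force.

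- **Evidence of poor recording.** The protocol nowhere says that LTOCS status was poorly recorded or that its recording changed. The expectation of change concerns the set of key variables as a whole. Appendix 1 makes LTOCS status a core variable required at every visit, included in every schedule, among them the one for key prior reviews before 2023. Retrospective correction by sites (Section 3) may also have flattened any gradient by visit year. This stands: the size is unknown and may be small.
- **Separating recording from practice.** Section 6.3 extends historical snapshots to all objectives except 4, although Section 3 names only Objectives 1 and 2. Comparing one visit year across snapshots shows changes in recording. This stands, so it would be too strong to say that a recording effect cannot be separated from a practice effect.
- **Recognition in the plan.** Two checks are planned, and imputation or bounds may be left to an SAP that is not at hand. This stands in part. The exclusion is a stated protocol rule, the first check reaches only unknowns later filled in, the second is descriptive, and the protocol links neither to the estimate.
- **Which cohort.** The same bullet excludes patients with one visit and those not on LTOCS at baseline, which suits the stopping/reducing analysis in 3(ii). As written it covers all of Objective 3. If it is meant for 3(ii) only, the protocol should say so and state how unknowns are handled in 3(i). The 30% used above describes an all-comer denominator; the spurious odds ratio does not depend on that choice.

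A reader might infer that better recording by itself produces a false fall, or that the bias runs towards the result the registry hopes for. The documents support neither. Equal improvement in both groups gives no bias (scenario C), the reverse pattern gives a rise (scenario D), and nothing in the protocol fixes the direction.

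**Conclusion.** The point holds in limited form. A stated complete-case rule is applied to a variable that is a target of the completeness drive, and the trend is read along the same time axis. This can distort the LTOCS trend in either direction, or not at all. The distortion requires the ratio of recording in users to recording in non-users to change over time, which the documents neither show nor exclude. On the assumed rates the spurious odds ratio runs from 0.67 to 1.53, with 0.89 for a modest 10-point rise in recording among non-users. These are illustrations, not estimates for this registry. The planned checks are worth keeping, but they do not protect the estimate as the protocol stands. A change is worth making because the data needed are already held.

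**What to change.** Keep the known-only trend, and add to Section 6.3 (or the SAP) a prespecified sensitivity analysis for Objective 3(i):

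1. Keep patients or visits with unknown LTOCS status in the denominator.
2. Report the unknown share by year, country and data-capture method.
3. Show the trend with two-sided bounds: all unknowns counted as no, and all counted as yes.
4. Add a weighted or imputed estimate that uses the proportion on LTOCS among initially unknown records, taken from backfilled or snapshot data. State the assumption that the remaining unknowns resemble the backfilled ones.
5. Describe a change in LTOCS use as a change in practice only with these results shown beside it. Do not use the single bound with all unknowns counted as no as a pass/fail rule.

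Section 4.2 should also say which of its exclusions apply to 3(i) and which to 3(ii), and Sections 3 and 6.3 should agree on whether snapshots are used for Objective 3.

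The cost is about a paragraph of wording and a few extra runs. The downside is wider uncertainty in years with many unknowns.
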